### Standard of care procedures

Patients will have PCNL performed in standard fashion, without deviation from standard of care. Per the usual practice of the treating surgeon, percutaneous access into the kidney will be obtained either by

Interventional Radiology or by the operating surgeon. At time of surgery, urine from the renal pelvis, urine from the bladder, and the stone itself will be sent for culture. Placement of renal drainage devices (ureteral stents, nephrostomy tubes, nephroureteral stents) will be left up to the discretion of the surgeon. Post-operatively, the patients will be admitted to the hospital and monitored per usual clinical procedure. Pre-operative CBC, basic metabolic panel (chem 7) as well as Postoperative day 1, a CBC, basic metabolic panel (chem 7). further laboratory tests will be dictated by the patients' clinical status as per the standard of care—i.e. for patients that exhibit signs of sepsis such as tachycardia (>90/min), low systolic blood pressure (<90 mmHg), fever >38.3C, hypothermia <36C, altered mental status, respiratory rate>20 min or leukocytosis >12000 or leukopenia (<4000), further urine culture, blood culture and serum lactate will be obtained (as per standard of care).

The patient will be discharged from the hospital per the usual clinical protocols. Post-discharge the patient will be seen in clinic 1-12 weeks after surgery. Patients will undergo a non-contrast CT abdomen/pelvis, an abdominal plain radiograph, and/or a renal ultrasound during this postoperative period.

Demographic fields that will be obtained preoperatively include age, race, gender, ASA (American Society of Anesthesiologists) score (for comorbidity assessment), body mass index (BMI), and prior stone disease. Disease fields that will be obtained include stone size (maximal axial and coronal dimensions), degree of hydronephrosis (mild/moderate/severe), and history of diabetes mellitus, history of cardiac disease, hypertension, prior urinary tract infection, history of bowel diversion, or neurogenic bladder.

Perioperative fields will include OR (surgical) time, type of anesthesia, number of access tracts, use of internalized ureteral stent, nephrostomy tube, or nephroureteral stent, estimated blood loss, and intraoperative complications. Postoperative fields will include postoperative maximum body temperature, heart rate, respiratory rate, urine culture results, stone culture results, stone composition, white blood cell count, serum lactate, postoperative serum creatinine, need for admission to intensive care unit, hospital length of stay (LOS), and stone-free status at 1-12 weeks postoperative imaging. Patients will be followed during routine clinical visits as part of their continuing care.

### b. Data Collection

Data will be collected by each participating site and entered into a designated and shared REDCap (Research Electronic Data Capture) database. All patient specific information will be de-identified and the database will be password protected with access rights restricted to the lead investigator or their team at each site. Data collectors will be blinded from treatment allocation.

### c. Data Handling

The electronic data will be stored in the external REDCap database. This database will be saved at a separate server that allows the study staff from non-UCSD sites to contribute their database. Study staff will create the database and is responsible for analyzing the study data. The coordinator at each site will perform data entry.

#### d. Data Analysis

The summary statistics will be used to describe the data. Mean/95% confidence intervals will be reported for continuous variables, and frequency/percentage will be reported for nominal variables. The primary outcome, rate of postoperative sepsis, and the corresponding 95% confidence interval (CI) will be reported, and compared between the intervention and control groups at the for the postoperative period using a Chi-squared test. Secondary outcomes will include rate of nonseptic bacteruria, stone-free rate, and LOS and will be compared with using Chi-squared tests or t-test as indicated. The patient characteristics and outcomes between those who have one-year follow up records and those who do not will also be investigated. Using 2-sided P values, statistical significance will be set at  $p \le 0.05$ .

Sepsis will be defined by the 2012 International Guidelines for Management of Severe Sepsis and Septic Shock where 2 or more of the following variables are present and temporally associated

- Temp > 38.3 C or <36 C
- Heart Rate > 90/min (at least 12 hrs after surgery)
- Respiratory Rate > 20/min (at least 12 hrs after surgery)
- Altered mental status: defined as lack of orientation to either name, place, or time/date.
- Systolic Blood Presure (SBP) < 90 mmHg, Mean Arterial Pressure < 70 mmHg, or SBP decrease >40 mmHg in adults
- WBC >12000 or < 4000

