### Treatment Assignment:

Patients will be assigned to control or intervention arm based on a predetermined allocation sequence that will be generated by a computerized random number generator. Patients will be stratified by institution in permuted blocks of varying size. Only study staff at the coordinating institution (UCSD) will have access to the full allocation sequence. i.e. no clinical staff involved in recruiting and consenting patients for the study at UCSD or other participating institutions will have knowledge of the allocation sequence at their institution prior to enrollment of each patient. To further aid allocation concealment, the block size will be varied.

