# f. Strengths

This study is unique in that it randomizes patients at low to moderate risk of postoperative infection and it uses the most updated definition of sepsis as the primary outcome. The limitations of previous studies have been a lack of randomization, exclusion of patients at moderate-high risk of infection, and less contemporary definitions of sepsis. It aims to answer very important and relevant questions as it pertains both to the surgical management of kidney stone disease and to the prophylactic use of preoperative antibiotics in patients with an increased risk of infection. It will also represent a broad geographic distribution of patients from the US and Canada due to the location of the participating sites.

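### Free improvement, not an error: the primary chi-squared test ignores institution, the randomisation stratum, and plausible baseline risk factors that the trial already collects

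*Combined protocol and SAP*

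**What the plan says.** Section d, Data Analysis, sets out the primary analysis: "The primary outcome, rate of postoperative sepsis, and the corresponding 95% confidence interval (CI) will be reported", and the rate is "compared between the intervention and control groups at the for the postoperative period using a Chi-squared test". The test is two-sided at 0.05. The section names no covariate, no stratified test and no adjusted sensitivity analysis. It attaches the interval to the rate and does not name a between-arm effect measure.

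Under Treatment Assignment: "Patients will be stratified by institution in permuted blocks of varying size". Institution is the only stratification factor, so no patient-level factor is balanced by design.

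The later of the two sections headed Standard of care procedures lists the baseline fields. They include "history of diabetes mellitus, history of cardiac disease, hypertension, prior urinary tract infection, history of bowel diversion, or neurogenic bladder", besides the stone's dimensions, a grade for hydronephrosis, demographics, ASA score and BMI.

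Section f, Strengths, describes the population as mixed: "it randomizes patients at low to moderate risk of postoperative infection".

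**The concern.** Two kinds of available information go unused. The first is institution: the design constrains the arms to be balanced within site, and the usual practice is to carry that stratification into the analysis. The second is the set of baseline fields that could bear on infection. If some of them predict sepsis, an unadjusted comparison gives up precision, and a chance imbalance stays in the estimate.

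There is also a matter of credibility. If an imbalance in, say, prior urinary tract infection appears, the plan offers only the unadjusted result. Any adjusted analysis would then be chosen from more than a dozen collected fields, possibly with outcomes already known. Naming a few covariates now closes off that choice.

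**Working it through.** The documents state no sample size, power, expected sepsis rate or effect size, so there is no figure of the plan's own to reproduce. Every rate, arm size and covariate strength below is an assumption.

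**1. Is the planned test valid?** With 15% sepsis in both arms, one binary factor (prevalence 25%, OR 2 or 4), 60, 100 or 200 per arm and 2,500 trials per setting, simulated type I error was 4.5% to 5.7% for chi-squared and 4.7% to 5.6% for the adjusted likelihood-ratio test. The planned test is valid.

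**2. How likely is a visible imbalance?** For a factor with 30% prevalence and n per arm, the probability of a gap of at least 10 points is 2 × [1 − Φ(0.10 / √(2 × 0.3 × 0.7 / n))].

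| n per arm | SE of the gap | z | Probability |
|---|---|---|---|
| 60 | 0.0837 | 1.20 | 23% |
| 100 | 0.0648 | 1.54 | 12% |
| 150 | 0.0529 | 1.89 | 6% |

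**3. What would such a gap do?** Take 15% sepsis overall and 30% prevalence. Solving 0.3·p₁ + 0.7·p₀ = 0.15 gives p₀ = 12.1%, p₁ = 21.7% for OR 2, and p₀ = 10.4%, p₁ = 25.8% for OR 3. A gap of exactly 10 points moves the risk difference by 0.10 × (p₁ − p₀), that is 0.95 points (OR 2) or 1.5 points (OR 3). At 100 per arm with 15% vs 5%, the SE of the risk difference is √[(0.15 × 0.85 + 0.05 × 0.95) / 100] = 4.2 points. The shift is therefore about 0.2 to 0.4 SE.

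The next check was a simulation with no treatment effect, 100 per arm and 400,000 trials per setting, keeping only trials where prior infection was at least 10 points lower in the nitrofurantoin arm. The unadjusted difference favoured treatment by about 1.2, 2.0 and 2.4 points for OR 2, 3 and 4. False claims of benefit occurred in roughly 4%, 5% to 6% and 6% to 7% of those trials, against a nominal 2.5%. A test stratified by prior infection stayed at about 2.5%. Over all trials, both tests kept about 5%.

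**4. How much power is gained?**

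- *One binary factor, 15% vs 7%*, unadjusted to adjusted:

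| n per arm | OR 2 | OR 4 |
|---|---|---|
| 60 | 29% to 31% | 28% to 31% |
| 100 | 45% to 45% | 44% to 47% |
| 200 | 74% to 76% | 73% to 76% |

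- *Three covariates, about 15% vs 5%, 100 per arm, score test, 6,000 trials* (two binary factors at 30% and 25%, one normal covariate with half the log OR): 67% to 67% with ORs of 2, and 61% to 65% with ORs of 3.
- *Large-sample variance ratio*, adjusted over unadjusted, for one normal risk score. The unadjusted variance is 2[p_c(1 − p_c) + p_t(1 − p_t)]. The adjusted one replaces each term by its mean over the score and adds the variance of the individual risk differences.

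| Sepsis rates | OR per SD 1.5 | 2 | 3 |
|---|---|---|---|
| 10% vs 5% | 0.99 | 0.96 | 0.91 |
| 15% vs 7% | 0.98 | 0.95 | 0.89 |
| 20% vs 10% | 0.98 | 0.94 | 0.87 |
| 30% vs 15% | 0.97 | 0.93 | 0.84 |

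The saving is about 1% to 7% for weak to moderate scores, and 9% to 16% only for a very strong one.

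**5. How should institution enter?** With seven equal sites assumed and 15% sepsis in both arms, a score test with three covariates plus institution as fixed effects gave type I error of 6.1% and 6.6% at 60 per arm (ORs 2 and 3), and 6.6% and 5.7% at 100 per arm. The chi-squared test gave 5.0%, 5.0%, 6.0% and 4.4% in the same settings (4,000 trials each, Monte Carlo SE about 0.35 points). A Mantel-Haenszel test stratified by site held about 4.5% to 5.2% at 60 and 100 per arm. Stratifying by one factor changed power by no more than about 1 point. Crossing site with prior infection lost 1 to 4 points.

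**The case against.** The best case against acting is that nothing is broken. Randomisation justifies the chi-squared test, chance imbalance is not bias averaged over randomisations, and the confidence interval already allows for it. The expected shift is a fraction of one standard error, and the power gain may be nil. With few events, about 20 at 100 per arm (15 + 5), a model carrying covariates and many site terms can be less trustworthy than the simple test.

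Most of this stands. It rules out calling the plan wrong, and it rules out a primary model with institution as many fixed effects. It does not rule out a site-stratified test, which kept its error rate, or a small covariate set named in advance. The argument about averages also does not settle how to read the one trial that is run, as the conditional results in step 3 show.

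A reader might infer that strong predictors of sepsis are being discarded, or that a trial of this size is especially exposed. The documents support neither reading: they give no prognostic strength for any field, describe the patients as low to moderate risk, and state no sample size.

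**Conclusion.** The point holds as a free improvement. The primary comparison is valid but uses neither the randomisation stratum nor any of the plausible risk factors recorded at baseline. The likely gain from covariate adjustment is about 0 to 4 points of power under assumed sepsis rates of 15% vs 5% or 7% and assumed odds ratios of 2 to 4. Stratifying by institution alone changes power very little; its merit is that the analysis follows the design. The main return comes from the pre-specified adjusted analysis, which guards the estimate against an unlucky draw and fixes the covariates before outcomes are known. An inference that the planned test inflates the error rate would be wrong, because it holds about 5% overall. The size cannot be narrowed further until a sample size, the number of sites and an expected sepsis rate are stated.

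**What to change.** In section d, Data Analysis:

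1. Make the primary test a Cochran-Mantel-Haenszel test stratified by institution, and report the Mantel-Haenszel risk difference with its 95% CI.
2. Before outcomes are seen, pre-specify one adjusted analysis with two or three named baseline covariates, for example prior urinary tract infection, diabetes and stone size. Use Firth-penalised logistic regression and report a standardised risk difference with its 95% CI. Handle institution by stratification or conditioning, not by many fixed effects. A conditional likelihood yields no predicted risks, so the text should say how the standardised difference is obtained. Firth estimation pulls fitted risks upwards when events are few, so the intercept should be recalibrated first. The Firth version was not among the tests simulated here, so its error rate should be checked once the arm size and number of sites are known.
3. Keep the unadjusted chi-squared result as a supporting analysis.

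The cost is a few sentences and slightly more programming, with no new data. The covariates must be fixed in advance.

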# Standard of care procedures:

Patients will be identified based on clinic visits or hospital admission. All patients will be counseled on standard treatment options— extracorporeal shock wave lithotripsy (ESWL), percutaneous nephrolithotomy (PCNL) and ureteroscopy (URS). The discussion regarding treatment options and subsequent care will not deviate from routine care. Patients consenting for PCNL will be considered for enrollment into the study and will be enrolled to have data collected prospectively. Patients will be consented prior to prescription of antibiotics and to the surgery for collection of demographics, disease, perioperative, and postoperative data. Abdominal pelvic computed tomography (CT), if not already obtained, will be used to delineate pre-operative stone size and for preoperative planning. If the patient does not consent to the study the use of antibiotics will be based on the routine clinical practice of the treating urologist. Both prophylaxis with preoperative antibiotics and no prophylaxis (i.e. periprocedural only) are considered standard of care and this study will examine the difference between these two common practices.

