# e. Feasibility and Time Frame

This study enrollment period will be 2 years, with presumed enrollment expected to be completed prior to that date. Each site is a high-volume stone center that performs more than 30 PCNLs per year.

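### The sepsis comparison names no between-arm effect estimate with a 95% CI, and its chi-squared test ignores the institutions by which randomisation is stratified

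*Combined protocol and SAP*

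**What the plan says.** The analysis of the primary outcome is set out in section d (Data Analysis). It first says "The primary outcome, rate of postoperative sepsis, and the corresponding 95% confidence interval (CI) will be reported". That interval belongs to the rate. The arms are then to be "compared between the intervention and control groups at the for the postoperative period using a Chi-squared test", two-sided, with significance at p ≤ 0.05. The section names no measure of the difference between arms and no interval for one. For the secondary outcomes it lists nonseptic bacteriuria, stone-free rate, and "LOS and will be compared with using Chi-squared tests or t-test as indicated".

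Two other places bear on this:

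- The first Standard of care procedures section states the aim. Giving and not giving preoperative antibiotics "are considered standard of care and this study will examine the difference between these two common practices".
- The Treatment Assignment section says "Patients will be stratified by institution in permuted blocks of varying size". Institution does not reappear in the analysis as a stratum, a covariate or a sensitivity analysis.

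**The concern.** **The estimate.** The study compares two accepted practices. A clinician choosing between them needs to know how large a benefit or harm is still possible, above all if the result is not significant. A p-value does not say. Separate intervals for each arm do not say either, because they can overlap when the interval for the difference excludes zero. The plan also leaves the choice of measure (risk difference, risk ratio or odds ratio) and of a crude or stratified analysis open until results are known.

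**The test.** When randomisation is balanced within institutions and sepsis risk differs between them, the ordinary chi-squared test overstates the variance of the comparison. Some difference between sites is plausible. The second Standard of care procedures section says renal drainage "will be left up to the discretion of the surgeon" and that afterwards "the patients will be admitted to the hospital and monitored per usual clinical procedure". These statements show that practice may vary. They do not show that sepsis rates differ by institution, and the documents give no rates.

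**Working it through.** The plan states no sample size, event rate or effect size, so there is no figure of its own to reproduce. All counts, rates and site sizes below are assumptions. Section e says "Each site is a high-volume stone center that performs more than 30 PCNLs per year", but that is surgical volume and not enrolment, so it does not fix the number of patients per site.

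**1. What a p-value leaves out.** For rates p₁, p₀ with n per arm, the 95% CI for the difference is (p₁ − p₀) ± 1.96 √[p₁(1−p₁)/n + p₀(1−p₀)/n].

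| Assumed counts | p | 95% CI for the difference (points) |
|---|---|---|
| 6/50 v 6/50 | 1.0 | ±12.7 |
| 15/100 v 15/100 | 1.0 | ±9.9 |
| 24/160 v 24/160 | 1.0 | ±7.8 |
| 12/100 v 15/100 | 0.535 | −12.5 to +6.5 |

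In the last row:

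- Risk difference: 1.96 √(0.1056/100 + 0.1275/100) = 9.5 points around −3.0.
- Risk ratio: 0.80 (0.39 to 1.62).
- Odds ratio: 0.77 (0.34 to 1.75).

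Separate arm intervals are no substitute. For 15/100 v 6/100 they are 8.0-22.0% and 1.3-10.7%, which overlap, yet the difference is 9.0 points (0.6 to 17.4).

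**2. Why ignoring institution makes the test conservative.** With arms balanced within site, the test assumes variance p̄(1−p̄) per patient, while the true variance omits the spread of rates between sites. For k sites evenly spaced over a range R, that spread is (R²/12)(k+1)/(k−1). In large samples the type I error is then 2[1 − Φ(1.96/√r)], where r is the true variance divided by the assumed variance.

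- 8 sites, 5-25%: the spread is (0.20²/12)(9/7) = 0.0043 and p̄(1−p̄) = 0.15 × 0.85 = 0.1275. So r = 0.966 and the type I error is about 4.6%.
- 8 sites, 2-40%: the spread is (0.38²/12)(9/7) = 0.0155 and p̄(1−p̄) = 0.21 × 0.79 = 0.1659. So r = 0.907 and the type I error is about 4.0%.

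**3. Simulation.** The uncorrected chi-squared test was compared with the CMH statistic z = Σ(x₁ₖ − n₁ₖmₖ/Nₖ) / √Σ[n₁ₖn₀ₖmₖ(Nₖ−mₖ) / (Nₖ²(Nₖ−1))]. Here site k has Nₖ patients and mₖ events. Each setting had 200,000 trials, equal arms within site, control rates evenly spaced over the range, and a common odds ratio of 1.0 (type I error) or 0.45 (power). Monte Carlo standard errors are about 0.05 and 0.11 points.

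| Sites × patients | Control rates | Type I error, chi-squared v CMH (%) | Power change with CMH (points) |
|---|---|---|---|
| 8 × 40 | all 15% | 4.9 v 5.0 | −0.3 |
| 8 × 40 | 10-20% | 4.8 v 5.0 | −0.1 |
| 8 × 40 | 5-25% | 4.5 v 4.9 | +0.6 |
| 8 × 40 | 2-40% | 4.0 v 5.0 | +2.9 |
| 4 × 40 | 5-25% | 4.3 v 4.9 | +1.0 |
| 4 × 40 | 2-40% | 3.8 v 5.0 | +4.3 |
| 8 × 12 | 10-20% | 5.4 v 4.9 | −1.8 |
| 8 × 12 | 5-25% | 5.1 v 4.9 | −1.1 |
| 7 × 12 | 5-15% | 5.8 v 5.1 | −1.5 |

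Over all 25 settings the type I error was 3.8-5.8% for chi-squared and 4.8-5.1% for CMH. At 12 patients per site the power change turns to about +1 point if sites span 2-40%. A separate simulation with random site effects (96, 192 or 384 patients; 6 or 8 sites) gave 3.5-5.5% against 4.7-5.3%, and power changes between about −3 and +3 points.

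**4. The stratified estimate.** The Mantel-Haenszel risk difference is Σwₖdₖ/Σwₖ, where dₖ is the risk difference in site k and wₖ = n₁ₖn₀ₖ/Nₖ. With equal arms within sites wₖ = Nₖ/4, and the estimate equals the crude difference. Only the interval changes. At 8 × 40 and odds ratio 0.45, the full width, crude v stratified (Sato variance), is 13.7 v 13.5 points (5-25%) and 15.9 v 15.4 points (2-40%). Coverage at 8 × 40 is 94.8-95.9% crude and 94.8-95.0% stratified. At 12 per site it is 94.2-95.7% and 93.8-94.6%.

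**5. Small sites.** Sites of 62, 50, 38, 30, 21, 9, 6 and 4 (N = 220) were randomised in blocks of 4 with a truncated last block. CMH kept a type I error of 4.8-5.0% whether or not sites under 10 were combined, with power within 0.1 points.

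**The case against.** The strongest reply is that little is lost. If the rate and the size of each arm are reported, any reader can compute the crude difference and its interval, and with balanced arms the stratified estimate is the same number. The unstratified test is valid. A power gain near 3 points at 8 × 40 needs sites spanning 2-40%, a spread that nothing in the documents supports, and in very small trials the stratified test rejects slightly less often and its interval covers slightly less. On this view, stratified analysis belongs in a sensitivity analysis.

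Most of this stands, and it limits the weight of the second half of the point. Stratifying should not be presented as a power gain. What remains is that a measure worked out afterwards has not been fixed beforehand, and that CMH holds close to 5% whether or not sites differ, while chi-squared drifts to either side.

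Two further objections call for additions to the fix. The CMH test and the risk-difference interval can disagree near p = 0.05, so the plan should say which governs. And with a common odds ratio, site risk differences vary when control rates vary, so the plan should say what the pooled difference represents.

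**Conclusion.** The point holds. The plan names no between-arm estimate of the sepsis effect with a confidence interval, and its primary test leaves out the factor by which patients are randomised. The first gap is the more important, because a non-significant result could leave differences of roughly 8 to 13 points either way unexcluded at 50 to 160 patients per arm with sepsis at 12-15%. The second is a modest mismatch: the type I error of the chi-squared test stays between about 3.5% and 5.8% across everything tried, and power moves by a few points at most. Neither gap invalidates the trial. Both should be closed because it is cheap to do so. The sizes rest on assumed rates, site numbers and site sizes. The two gaps themselves rest on the text alone.

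**What to change.** In section d:

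1. Name the effect estimate: the risk difference in sepsis, stratified by institution (Mantel-Haenszel), with its 95% CI. Describe it as a weighted average of the site differences.
2. Make the primary test a Cochran-Mantel-Haenszel test stratified by institution, and state that it governs significance if the interval disagrees. Fix a rule for very small sites before analysis, for example combining sites with fewer than 10 randomised patients into one stratum.
3. Optionally, treat the binary secondary outcomes the same way and put site as a factor in a linear model for length of stay. For stone-free rate at 8 × 40 and odds ratio 2, the power gain was 0.1 points with all sites at 75% and 1.7 points with sites at 60-90%. For length of stay (assumed normal, difference 0.3 SD), power was the same if site explains none of the variance, and 80.8% v 77.7% if it explains 10%. Nonseptic bacteriuria was not simulated.

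The cost is two or three sentences and a few lines of code. Institution is already known for every patient. The statistical price is about 0.3 points of power at 8 × 40 if sites do not differ. At about 12 patients per site there are about 1-2 points fewer rejections when sites differ moderately, partly because chi-squared there exceeds 5%. The separate simulation at 96 patients showed a loss of up to about 3 points.

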### g. Limitations

The inclusion of a placebo pill would strengthen the study but was not able to be included due to logistical difficulties with obtaining a placebo of identical appearance that would have been adequate for blinding. Furthermore, there is little benefit of a "placebo effect" for the objective outcomes that we seek to study which are signs and symptoms of sepsis and septic shock.

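### Nonseptic bacteriuria is tested between arms without saying which culture counts, and follow-up completeness is examined at one year although the stone-free rate is read at 1-12 weeks

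*Combined protocol and SAP*

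**What the plan says.** **Outcome.** Section d. Data Analysis of the combined protocol and SAP lists the secondary outcomes: "Secondary outcomes will include rate of nonseptic bacteruria, stone-free rate, and LOS". They are to be compared by chi-squared or t-test at a two-sided 0.05 level. No specimen, collection time, growth threshold or denominator is given for bacteriuria. The same section defines sepsis sign by sign, "where 2 or more of the following variables are present and temporally associated".

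**Cultures.** The perioperative part of Standard of care procedures provides two sources of urine culture:

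- At surgery, with no restriction to a subgroup: "At time of surgery, urine from the renal pelvis, urine from the bladder, and the stone itself will be sent for culture".
- After surgery, beyond the day-1 blood tests, "further laboratory tests will be dictated by" the patient's condition. The trigger opens with the words "for patients that exhibit signs of sepsis such as tachycardia (>90/min" and goes on to blood pressure, temperature, mental status, respiratory rate and white cell count. For these patients "further urine culture, blood culture and serum lactate will be obtained".

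The list of postoperative fields contains "urine culture results, stone culture results, stone composition" without saying which source the urine result comes from.

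**Blinding.** Section g. Limitations explains that there is no placebo because of the difficulty of "obtaining a placebo of identical appearance that would have been adequate for blinding". Section b. Data Collection blinds the data collectors and says nothing of the staff who order cultures.

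**Follow-up.** The only scheduled clinic visit is 1-12 weeks after surgery, and stone-free status is read from imaging in that window. Section d. Data Analysis plans to compare patients with and without one-year records.

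**The concern.** The two culture sources lead to different outcomes. A culture planned for every operated patient measures bacteriuria in a group that does not depend on what happens after surgery. A culture triggered by signs measures it only in patients who developed signs, and those signs are what the treatment is meant to prevent. The trigger sets no minimum number of signs, and it lacks the 12-hour delay that the sepsis definition puts on heart and respiratory rate. Some nonseptic patients will therefore be cultured and others will not. If that share differs by arm, the recorded rate can differ when bacteriuria does not, or can hide a real difference.

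The word 'nonseptic' adds a second difficulty under either source: it makes the secondary outcome depend on the primary endpoint.

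For the stone-free rate, what matters is who lacks the 1-12 week imaging. A comparison by one-year records does not describe those patients.

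**Working it through.** The plan gives no bacteriuria rate, sepsis rate, sample size or imaging completeness, so there is no figure to reproduce. **Every rate below is assumed.** Control is given first; ratios are intervention over control.

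**1. Which source is meant.** The field list calls the urine result postoperative, but it lists stone culture beside it, and the only planned stone culture is at surgery. The label therefore does not settle the source.

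**2. Sign-triggered cultures.** Let b be true nonseptic bacteriuria, 15% in both arms. Let t1 and t0 be the chances of being cultured with and without bacteriuria. Septic patients are left out, so that only culturing differs.

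- Rate over all patients = b × t1
- Rate among the cultured = b × t1 / (b × t1 + (1 − b) × t0)

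| Culturing (t1/t0), control v intervention | Over all patients | Ratio | Among cultured | Ratio |
|---|---|---|---|---|
| 30%/30% v 20%/20% | 0.15×0.30 = 4.5% v 0.15×0.20 = 3.0% | 0.67 | 15% v 15% | 1.00 |
| 20%/20% v 30%/30% | 3.0% v 4.5% | 1.50 | 15% v 15% | 1.00 |
| 50%/20% v 40%/20% | 7.5% v 6.0% | 0.80 | 0.075/0.245 = 30.6% v 0.060/0.230 = 26.1% | 0.85 |
| 50%/20% v 50%/15% | 7.5% v 7.5% | 1.00 | 30.6% v 0.075/0.2025 = 37.0% | 1.21 |

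Equal culturing in both arms gives 1.00 on either denominator. The cultured-only denominator removes the distortion when culturing is unrelated to bacteriuria, but not otherwise.

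**3. At-surgery cultures, all operated patients.** With b the share bacteriuric and s the sepsis risk given bacteriuria, nonseptic bacteriuria = b × (1 − s). Take true bacteriuria as 20% v 13.3% (ratio 0.67).

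- s = 30% v 30%: 0.20×0.70 = 14% v 0.1333×0.70 = 9.3%, ratio 0.67.
- s = 20% v 10%: 0.20×0.80 = 16% v 0.1333×0.90 = 12%, ratio 0.75.
- s = 30% v 15%: 0.20×0.70 = 14% v 0.1333×0.85 = 11.3%, ratio 0.81.

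Each result is the correct rate of bacteriuria without sepsis. It equals the relative effect on bacteriuria only when s is the same in both arms.

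**4. Missing imaging.** Suppose 60% of imaged patients are stone-free in both arms and a share m lacks imaging. The rate in an arm lies between 0.60(1 − m) and 0.60(1 − m) + m.

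- m = 10%: 54% to 64% per arm, so the arm difference lies between −10 and +10 points.
- m = 20%: 48% to 68% per arm, so between −20 and +20 points.
- If 40% v 80% of the unimaged are stone-free, m = 10% gives 58% v 62% (4 points) and m = 20% gives 56% v 64% (8 points).

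**The case against.** The strongest reply is that the bias depends on a reading the plan never states. The at-surgery reading fits the text equally well, and with all operated patients in the denominator it gives a valid comparison of the outcome as named. That stands.

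On the sign-triggered reading, most of the triggers are numeric, the cultures are directed and not optional, and nothing suggests ordering by arm. If treatment reduces signs, fewer sign-plus-culture cases is a real effect on clinically detected bacteriuria. This also stands, but it describes a different outcome, and the plan does not say that it is the one intended. The lack of a placebo leaves open, without showing, that knowledge of the arm affects ordering.

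A reader might go further and infer that the comparison will favour the intervention. The documents do not support this: the table gives ratios below and above 1. Nor do they support a reversed effect under the at-surgery reading. One can be constructed (bacteriuria 20% v 18% with s = 30% v 15% gives 0.20×0.70 = 14% v 0.18×0.85 = 15.3%), but it needs a small fall in bacteriuria alongside a halved sepsis risk, both assumed. A denominator of nonseptic patients only would select on the primary endpoint, but the plan does not propose it.

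On follow-up, the one-year comparison is not presented as the missing-data check for the stone-free rate, and routine visits may produce one-year records. Imaging is planned for all patients, and the bounds in step 4 are worst-case arithmetic for any outcome with that much missing. These replies justify keeping the one-year comparison as an extra. They do not supply a check at 1-12 weeks.

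**Conclusion.** The point holds in a limited form. The plan tests an outcome whose validity depends on an unstated choice of culture. With sign-triggered cultures over all patients, the result mixes culturing with bacteriuria. With at-surgery cultures over all operated patients, it is valid for bacteriuria without sepsis but does not measure the effect on bacteriuria as such. The documents do not show that the trial's comparison is biased, and neither direction nor size can be derived from them; the figures above only illustrate the mechanism.

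The follow-up comparison is set at a time for which no visit or outcome is scheduled, and no check is specified for missing 1-12 week imaging. How much imaging will be missing is unknown.

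Both parts concern secondary outcomes. The primary sepsis comparison is not affected.

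**What to change.** **Bacteriuria**

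- Name in advance one at-surgery urine specimen (bladder or renal pelvis), its growth threshold, and all operated patients as the denominator. Report the other specimen descriptively: testing both at 0.05 allows a chance of at least one false positive of up to 0.05 + 0.05 = 10%.
- Compare bacteriuria regardless of later sepsis, and tabulate it by sepsis status in each arm so that the named outcome is still reported.
- Give the number randomized but not operated on per arm, since these patients have no culture.
- Report sign-triggered postoperative cultures descriptively, with the number cultured per arm.

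**Follow-up**

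- Compare, by arm, patients with and without the 1-12 week imaging, and add a missing-outcome sensitivity analysis for the stone-free rate. The one-year comparison may stay as an extra if such records exist.

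**Cost.** No new samples or imaging are needed, and the added analysis is small. The real cost is a change of target. Under Investigational portion of treatment, the oral course ends 1 day before surgery and is given in the intervention arm only, so the at-surgery culture reflects very recent oral antibiotic exposure in that arm. It describes urine at surgery, not later bacteriuria. If the sponsor intended a postoperative outcome, that outcome becomes descriptive.
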